The participants will be recruited when hospitalized at the Neurotraumatology Clinic of the Hospital das Clínicas Complex of the Medical School of the University of São Paulo (HCFMUSP). Overall admission and in-hospital records will be collected of each patient who meet the inclusion criteria. Patients will complete the minimum period of 6 months of TBI of follow-up.

In this study, REAC will be performed a single session of Neuro Postural Optimization (NPO), and 18 Neuro Psycho Physical Optimization – Brain Wave Optimization-G (NPPO-BWO-G) treatment sessions for 4 daily sessions. Each next of kin will receive written instructions with the date and time of the next sessions in order to avoid misunderstandings.

Search locations

The study will be conducted within the HCFMUSP, in São Paulo - SP, which has 2400 beds distributed among its 8 specialized institutes and 2 auxiliary hospitals (www.hc.fm.usp.br). The research locations in the various stages of the study are described in Table 6:

Table 6 - Stages of the study and the respective places where they will be carried out

Stage of the study	Location	Purpose
Patient selection	ICU - Neurotraumatology	
Electroencephalogram	ICU - Neurotraumatology	Brain waves mapping
Brain MRI	Central Institute	DAI diagnostic
REAC	ICU - Neurotraumatology	Intervention

DAI: diffuse axonal injury, ICU: intensive care unit, MRI: magnetic resonance imaging,

REAC: radio-electric asymmetric conveyer.

Study design

This is a prospective, randomized, double-blind, placebo-controlled clinical trial. According to the hypotheses of the present study, the sample size calculation was made considering an alpha error of 5% and based on other studies with similar design [135-140]. We estimate that 30 patients should complete the follow-up and be included in the statistical analyses. However, lack of adherence could be a problem. Thus, we estimate losses at 20% and calculated a final sample size of 36 participants. Subjects with no history of chronic neurological disorders will also be included and separated of DAI patients but submitted to the same protocols. After meeting the eligibility criteria, the participants will follow the steps of the study as described in Table 7.

Table 7 - The study steps

Patient selection	Medical record, radiology, participation consent
Step 1 (pre-intervention)	qEEG, TCD and brain4care up to 3 days before the start of REAC sessions
Step 2 (intervention)	NPO (single session)
Step 3 (intervention)	NPPO-GW (18 sessions)
Step 4 (post-intervention)	qEEG up to 3 days after the end of REAC sessions

Follow-up discharge, 3m and 6m mRankin, GOSE, DASS 21

qEEG: quantitative electroencephalogram, TCD: transcranial Doppler, REAC: radio-electric asymmetric conveyer, NPO: neuro-postural optimization, NPPO-GW: gamma-waves neuro psycho physical optimization.

Randomization

A participant will select patients according to DAI criteria and obtain consent for participation with the next of kin for each eligible patient. Following, qEEG examinations will be performed. Up to three days after finishing NPPO-BWO sessions, a second acquisition of qEEG will be performed. All participants will be blinded between active and sham until the study is finished.

Participants will be randomly divided in a 1:1 ratio into two groups:

1. Active
2. *Sham*

The randomization process will be done in blocks interchanged, with the size of each block equal to four. The computerized system available in www.randomization.com will be used. For the persistence of allocation concealment, all evaluations will be performed using a database containing the group with a label "A" and "B". Consequently, all analyses were made without possible presumptions as to the allocation of the group.

Masking of Groups

In order to maintain masking in the study, the REAC device has a very similar shape, size, color, weight and emits very similar sounds. The participants and their families will not know which group the patient has been included up to the conclusion of the study. The entire process of selection, interview, neuropsychological evaluation and intervention with REAC will be similar in the groups, differing only the type of device used. The neuropsychologist responsible for the application of the neuropsychological tests will be unaware of the allocation of the intervention group.

Ethics

The project will be submitted to the Research Ethics Committee of the Hospital das Clínicas da Faculdade de Medicina da Universidade de São Paulo.

All responsibles for the patients will have full knowledge of the objectives and methods of the experiment and consented through written signature of the informed consent form. They will be informed about the experimental character of the proposed intervention, expected risks and benefits, as well as their random inclusion in one of the treatment groups (active and *Sham*). They will be aware that they could request their exclusion from the research at any time, without this interfering on the care that this patient receives in the institution.

The study will be conducted according to the requirements of the institution's ethics committee and also based on the recommendations established in the Declaration of Helsinki (1964), as amended in Tokyo (1975), Venice (1983) and Hong Kong (1989).

The therapeutic application of REAC will be carried out according to the ethical principles established in the aforementioned declarations and in the ethics standards of the Ministry of Health (C.N.S. Resolution no. 196 10/10/96). The ethical foundations and guidelines for the clinical application of REAC followed the basic precepts of treatment with this technique according to the International Conference on REAC Safety Consensus, held in March 2008 in Siena, Italy.

This study will be registered in ClinicalTrials.Gov (www.clinicaltrials.gov), one of the most reliable sources of consultation on clinical studies in the world. This is the U.S. government agency responsible for centralizing and updating information about studies that have been registered on this platform and that are underway around the world.

Procedures

Quantitative Electroencephalogram

Purpose: Documenting brain waves patterns pre and post interventions.

Patients will be submitted qEEG testing before starting the REAC protocols and then after finishing the last session. For data collection, EEG examinations were performed using an international 10-20 electrode placement system. The examination will last 30 minutes, 15 minutes with eyes open and 15 minutes with eyes closed (relaxed wakefulness. The digital 19-channel Nihon Kohden® EEG 1200 version 01.71 (Nihon Kohden, Tokyo, Japan) will be used., The channels follow the 10-20 system: seven located in the frontal lobe (Fz, Fp1, Fp2, F3, F4, F7 and F8), three in the center (Cz, C3 and C4), four in the temporal lobe (T3, T4, T5 and T6), three in the parietal lobe (Pz, P3 and P4) and two in the occipital lobe (O1 and O2). For quantitative analysis, the data were converted using the Neuromap of the Neuroworkbench software, transferred to Matlab vR2002b and treated with the EEGLab v2023.0116 software. After being imported into EEGLAB, the spatial coordinates of each electrode will be inserted according to the 10-20 system. The signals were referenced using the average between the channels. The baseline was automatically removed using a 0.5Hz 117 high-pass filter. Artifacts are automatically rejected and incorrect data periods removed. Finally, the Independent Component Analysis is performed.

Processing

Using EEGLab's Darbeliai tool, the power spectral density of each channel is calculated for four bands: delta (1-4 Hz), theta (4-8 Hz), alpha (8-13 Hz), beta (13-32 Hz), in which the absolute power will be determined. The relative power analysis will be performed using the Fast Fourier Transform FFT.

OUTCOMES

Primary:

Observe if there are significant changes in the electroencephalographic pattern, compared between the groups.

Secondary:

Observe if there are:

Significant clinical improvement determined by the mRankin and GOSE scales between the groups.

Statistical analysis

Categorical variables will be presented in absolute values and relative frequencies, while continuous variables will be described in measures of central tendency and dispersion. All analyses will be performed under the intention to treat.

The Kolmogorov-Smirnov test will be used to verify the parametric nature of the quantitative values observed in the battery of neuropsychological tests. The repeated measures related to the items neuropsychological assessment and cortical excitability will be compared through ANOVA-type analyses (*analysis of variance*) of two factors for repeated measures and the interaction test between the groups considered to test the null hypothesis[141, 142].

To compare the delta (Δ) values between the intervention groups, the Mann-Whitney test will be used. The comparison of the frequency of adverse effects according to the intervention groups will be performed using Pearson's chi-square. The Wilcoxon Rank-Sum test will be performed in the intra-group comparison regarding pre-intervention (E1) and post-early intervention (E2) performance in the neuropsychological assessment.

Statistically significant findings are those with a p-value or probability of type I error lower than 5%. The control of blinding will be done with the analysis of agreement with Cohen's kappa. The sample size is based on the TMT part B scores obtained after the intervention (E2). The analyses were performed using *Microsoft Excel* 2010 and *IBM SPSS (Statistical Package for Social Sciences)* v.21.0.

Funding

The present study will receive no funding. Device/software manufacturers will support the project providing their methods to be used in the study.

Chronogram

June 2024- Protocol submission.

Recruitment: One year.

Data analysis: Three months.

Publishing results: Manuscript submission to publication one month later.

References

1. Ghajar J. (2000) Traumatic brain injury. Lancet 356:923-929. [https://doi.org/10.1016/S0140-6736\(00\)02689-1](https://doi.org/10.1016/S0140-6736(00)02689-1)
2. Cole TB. (2004) Global road safety crisis remedy sought: 1.2 million killed, 50 million injured annually. JAMA 291:2531-2532. <https://doi.org/10.1001/jama.291.21.2531>

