EFFECTS OF RADIO ELECTRIC ASYMMETRIC CONVEYER (REAC) NEUROBIOLOGICAL
TREATMENTS IN DIFFUSE AXONIAL INJURY: A RANDOMIZED, DOUBLE-BLIND CLINICAL
TRIAL

Unique Protocol Id: 84791824.8.0000.0068

Date: October/15/2025

Abstract

Background: Severe traumatic brain injury, particularly diffuse axonal injury (DAI), often leads to lasting neurological issues. Cerebral dysfunction in DAI can be evaluated by monitoring cerebral electrical activity (CEA) through EEG. The radio electric asymmetric conveyer (REAC) is a noninvasive method designed to rebalance cellular polarity via endogenous bioelectric fields and modulate CEA. This technique may alter CEA, which can be detected using quantitative EEG (qEEG).

Objective: To assess qEEG changes following DAI and brain wave alterations after a REAC protocol in this group.

Methods: In this prospective, randomized, double-blind clinical trial, adult (≥ 18 y.o.) DAI patients will be assigned to active or sham groups for 19 sessions of either true or sham REAC following ICU discharge. Interventions include one Neuro Postural Optimization session and 18 NPPO-BWO-G sessions (up to four per day). The main outcome is to evaluate changes in qEEG patterns through population brain electrical mapping after REAC therapies. Additionally, voluntary adults (≥ 18 y.o.) with no history of neurological diseases will be submitted to the same protocol to further comparisons between qEEG patterns.

Keywords: cognitive dysfunction; diffuse axonal injury; radio electric asymmetric conveyer; rehabilitation; traumatic brain injury.

LIST OF ACRONYMS AND ABBREVIATIONS

ANOVA.....	analysis of variance
ANP	neuropsychological assessment
BDNF.....	brain-derived neurotrophic factor
Beta-APP.....	Beta-Amyloid-Precursor-Protein
BVMT.....	Brief Visuospatial Memory Test
CE	cortical excitability
CRT	cognitive rehabilitation therapy
CONSORT	Consolidated Standards of Reporting Trials
cTBS.....	continuous theta burst stimulation
DAI.....	diffuse axonal injury
DWI	diffusion weighted imaging
EEG.....	electroencephalogram
EMP	motor evoked potential
FIC	intracortical facilitation
GABA	gamma-aminobutyric-acid
GRE.....	gradient echo
HVLT	Hopkins verbal learning test
LAT	traumatic axonal injury
LED	Light-Emitting Diode
LLLT	Low Level Light/Laser
LM	Resting Motor Threshold
LTD	Long-Term Depression
LTP.....	Long-Term Potentiation
M1.....	primary motor area

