MRI.....	magnetic resonance imaging
MSC	minimum state of consciousness
NMDA.....	N-Methyl-D-Aspartate
PDC.....	prefrontal dorsolateral cortex
PET	positron emission tomography

PVS	persistent vegetative state
RCT	randomized clinical trial
STAITER.....	state-trait anxiety inventory
SIII	short interval intracortical inhibition
TC	computed tomography
TBI	traumatic brain injury
TD	diffusion tensor
TF3D	three-dimensional fiber tractography
TMT	trail making test

LIST OF UNITS

µA	microAmpere
Cm	centimetre
Ms	millisecond
°C	degree Celsius
T	Tesla
Db	decibel
Mv	milliVolt
Hz	Hertz
V	Volt
m	meter

LIST OF FIGURES

Figure Y. Evaluations and interventions performed during the study.

Figure X CONSORT flow diagram

INTRODUCTION

Traumatic brain injury (TBI) is a leading cause of death and disability globally, significantly affecting the quality of life for patients and caregivers [1-3].

In the United States, traumatic brain injury is the leading cause of death for people aged 1 to 45 and a major risk factor for morbidity and mortality in polytrauma cases [4].

Although epidemiological data in Brazil are limited, studies indicate that TBI is a significant public health issue, primarily impacting the country's young and economically active population [5, 6].

Automobile accidents and falls are primary causes of traumatic brain injury, with incidence rates highest among young adults (20 to 29 years) and individuals over 80 years old [4-6].

TBI is a highly heterogeneous condition, with multiple classification systems that emphasize distinct aspects such as the underlying mechanism of injury, clinical severity, radiological characteristics, and pathophysiological processes. These classifications play an important role in standardizing data collection, identifying prognostic factors, and informing the selection of appropriate therapeutic approaches tailored to individual cases.

From a pathophysiological perspective, traumatic brain injury (TBI) causes damage through primary lesions—direct energy transfer to the brain at trauma—and secondary effects, which involve cellular and molecular changes occurring for hours to weeks post-injury [7, 8].

Diffuse axonal injury (DAI) is a type of lesion in TBI that leads to significant brain dysfunction and affects roughly 40% of patients, making it a leading cause of neurological problems in survivors [9-11].

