Clinically, it is defined as a coma lasting more than 6 hours after TBI, excluding cases caused by ischemic brain injury or intracranial masses [10, 12]. Gennarelli et al.'s 1982 study described DAI in primates as a range of injuries mainly involving brain white matter

damage [9]. In 1989, Adams established objective criteria for classifying DAI from an anatomicopathological perspective into three categories: mild, moderate, and severe [10]. In each case, the principal form of structural damage is axonotmy (axon injury), which may occur immediately at the time of trauma (primary) or subsequently (secondary), following a series of biomolecular events [13-15].

Detecting this condition during routine exams in TBI patients can be challenging, as DAI-related abnormalities are often missed by standard CT or MRI scans and may require advanced imaging techniques to identify structural changes in the central nervous system [16-23].

From a neurological perspective, TBI can result in a wide range of cognitive, behavioral, and sensory-motor changes that may affect the patient's quality of life. Cognition encompasses the processes involved in acquiring knowledge and includes factors such as thought, language, memory, reasoning, and task execution, which are considered important for intellectual development [24, 25].

Although TBI is strongly linked to cognitive dysfunction, effective treatment remains difficult. While cognitive rehabilitation therapies have shown benefits in some studies, results are inconsistent [26-29].

Drug therapies for post-TBI cognitive disorders have proven ineffective [30]. The limited effectiveness of conventional cognitive rehabilitation in DAI patients has led to the exploration of new therapies. Neuromodulation techniques, both invasive and noninvasive, offer promising options by targeting specific brain regions to alter activity and support recovery.

Radio electric asymmetric conveyer (REAC) technology is a noninvasive technique that was first described by Rinaldi and Fontani [31, 32]. REAC neurobiological modulation with specific protocols such as neuro-postural-optimization (NPO) and neuro-psychophysical-optimization – brain wave optimization-G (NPPO-BWO-G) is a safe, established technique with proven therapeutic benefits for various neurological and psychiatric disorders [33-40].

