Given the significant brain damage and multiple disabling neurological sequelae, in severe TBI patients, combined with the limited efficacy of conventional pharmacological and cognitive rehabilitation interventions, REAC may be a promising therapeutic approach for affected patients. We will conduct a randomized clinical trial to assess REAC's effects in patients with DAI.

GOALS

Primary Endpoint

- To evaluate the qEEG changes in patients with subacute/chronic DAI, following REAC neuromodulation.

Secondary Endpoint

- To evaluate the qEEG changes in adults free of neurological conditions, following REAC neuromodulation.
- To evaluate cognitive and humor changes in adults free of neurological conditions, following REAC neuromodulation.

LITERATURE REVIEW

TBI Classifications

TBI is typically a heterogeneous condition being classified by clinical severity, mechanism of injury and pathophysiology, all of which are relevant to properly determine treatment and prognosis.

From a clinical point of view, TBI is classified as mild, moderate and severe depending on the duration of the loss of consciousness, level of consciousness on the Glasgow Coma scale and the presence or absence of post-traumatic amnesia, as well as its duration. However, knowledge of other information, such as history of exogenous intoxication, use of sedatives and neuromuscular blockers, as well as orotracheal intubation, is essential to avoid misclassification of TBI [41, 42].

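### The schedule in Table 7 does not carry the neuropsychological tests that the masking and statistics sections rely on, and gives the volunteers' cognition and mood endpoint no named measure and no pre-treatment value

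*Protocol*

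**What the plan says.** **Volunteers.** Under Goals, one secondary endpoint reads "To evaluate cognitive and humor changes in adults free of neurological conditions, following REAC neuromodulation" (we take *humor* to mean mood). Study design adds: "Subjects with no history of chronic neurological disorders will also be included and separated of DAI patients but submitted to the same protocols". The sentence after that sends participants to Table 7 for the study steps. The abstract gives the volunteers a narrower purpose: they are adults "with no history of neurological diseases will be submitted to the same protocol to further comparisons between qEEG patterns".

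**Schedule.** Step 1 of Table 7 is "qEEG, TCD and brain4care up to 3 days before the start of REAC sessions". Steps 2 and 3 are the REAC sessions. Step 4 is a second qEEG within 3 days of the last session. Follow-up has mRankin, GOSE and DASS 21 at discharge, 3 months and 6 months.

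**Masking and statistics.** Masking of Groups says that neuropsychological evaluation runs alike in both groups and that the neuropsychologist does not know the allocation. Statistical analysis checks the distribution of a neuropsychological battery. It applies a two-factor repeated-measures ANOVA to neuropsychological assessment and cortical excitability, and compares E1 (pre-intervention) with E2 (early post-intervention) within groups. It states that the sample size rests on TMT part B at E2. Study design says only that "the sample size calculation was made considering an alpha error of 5% and based on other studies with similar design".

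**Outcomes.** The primary outcome is the EEG pattern. The secondary outcomes are mRankin and GOSE.

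**The concern.** A change after treatment needs a value before it. Staff who follow Table 7 would record no cognitive test from anyone and no mood scale from volunteers before treatment. An analysis plan written later can choose a method but cannot recover a baseline that was not collected.

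Two things are at stake: a declared secondary endpoint in volunteers, and a set of planned analyses that includes the score said to justify the sample size. That score, TMT part B, is neither a listed outcome nor an entry in Table 7.

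**Working it through.** No power calculation bears on this. The check sets the sections side by side.

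**1. Table 7, row by row.** There are 6 rows: patient selection, Steps 1 to 4, and follow-up.

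| Measure | Rows of 6 | Visits bracketing treatment (Steps 1 and 4), of 2 |
|---|---|---|
| Neuropsychological test | 0 | 0 |
| Cortical excitability | 0 | 0 |
| DASS 21 | 1 (follow-up) | 0 |
| qEEG | 2 | 2 |

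DASS 21 has 3 time points. Discharge has no evident meaning for volunteers who are not inpatients, which leaves 3 − 1 = 2 (3 and 6 months).

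**2. What Statistical analysis expects.** Neuropsychological data are used 4 times: the Kolmogorov-Smirnov check, the two-factor ANOVA, the E1–E2 comparison and the TMT part B sample-size basis. Cortical excitability shares the ANOVA sentence. The Mann-Whitney comparison of delta values does not name its variable and is not counted.

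**3. Which instruments are named.** TMT part B is the only test named for E1/E2. The abbreviation list also holds BVMT, HVLT and a "state-trait anxiety inventory", but the methods do not use them.

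**4. Do the volunteers have a baseline?** The phrase about the same protocols can be read in three ways.
- *The steps of Table 7.* The sentence that follows it favours this. No mood or cognitive value is then listed at Step 1 or Step 4.
- *The REAC sessions only.* The Introduction uses the word *protocols* for the treatments. Volunteers then have no stated assessment schedule.
- *The whole study process, E1/E2 included.* A cognitive baseline is then intended, but apart from TMT part B the battery is undescribed, and Table 7 does not list it.

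Only the third reading gives a pre-treatment value, and it relies on text that Table 7 does not support.

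**5. The sample-size figure.** The step from 30 completers to 36 participants is 30 × (1 + 0.20) = 36. The 30 cannot be traced to TMT part B, since no difference, standard deviation or power is given for that score. This point does not depend on that; it concerns whether the score will be collected.

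**The case against.** The strongest reply is that testing is plainly intended. Masking of Groups assigns it to a blinded assessor, and Statistical analysis labels E1 as pre-intervention and E2 as early post-intervention, so a baseline time point for cognition is stated. The list of figures also names a Figure Y, "Evaluations and interventions performed during the study", which is not visible and may hold a fuller schedule. This stands. It rules out two inferences that a reader might draw: that the tests are scheduled for no participant, and that the volunteers have no baseline on any reading.

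It does not remove the mismatch. Study design points participants to Table 7, and the visible text mentions Figure Y only in the list of figures. If Figure Y adds tests, it differs from Table 7 and the two still need aligning.

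The second reply is that absence from Table 6, Procedures and Outcomes proves little. That is right. Table 6 gives locations, and Table 6 and Procedures also omit TCD, brain4care, mRankin, GOSE and DASS 21, all of which Table 7 schedules. Outcomes omits TCD, brain4care and DASS 21. The finding therefore rests on Table 7, with the added fact that the sample-size variable is not a listed outcome.

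Third, the two sample-size statements may look contradictory. They need not be: similar studies can be the source and TMT part B the variable.

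Finally, DASS 21 as the volunteers' mood measure is our inference. The Protocol names it once and never ties it to this endpoint.

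**Conclusion.** The point holds as an inconsistency within the visible text. Table 7 lists no neuropsychological or cortical-excitability measure in any of 6 rows, while Statistical analysis uses neuropsychological data 4 times and rests the sample size on one such score. The volunteers' cognition and mood endpoint has no named instrument, and the one candidate mood scale is scheduled at 0 of the 2 visits that bracket treatment. As Table 7 stands, that change cannot be formed unless the E1/E2 battery applies to volunteers or Figure Y adds a baseline.

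If volunteers are randomised and the follow-up row applies to them, active and sham could still be compared on DASS 21 from 3 months. That would not be the change from before treatment that the endpoint implies.

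A reader might also infer that the statistics text was carried over from another study. The documents do not establish this, and the point does not need it. The primary qEEG outcome is measured at Steps 1 and 4 and is not affected. The matter should be corrected, because following the schedule as printed would lose data that cannot be recovered.

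**What to change.** 1. **Volunteers.** State that the Table 7 assessments apply to them. Name the mood measure for the Goals endpoint (DASS 21, if that is intended) and enter it for volunteers at Steps 1 and 4.
2. **All participants.** Reconcile Masking of Groups and Statistical analysis with Table 7 in one of two ways.
   - *Keep the testing.* Name the E1/E2 tests, since only TMT part B is named now, and enter them at Steps 1 and 4 for each population in which they will be analysed. Include volunteers if cognition stays in their objective. Treat cortical excitability in the same way, or remove it.
   - *Withdraw it.* Delete the neuropsychological, E1/E2, TMT part B and cortical-excitability text and take cognition out of the volunteers' objective. Point the stated tests at the qEEG outcome, and restate the sample-size basis on an outcome that the trial measures.
3. If Figure Y already shows these assessments, bring Table 7 into line with it.

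**Cost.** For volunteers, a short questionnaire at the pre- and post-treatment qEEG visits, plus wording. If cognition is kept, the test sessions that Masking of Groups and Statistical analysis already assume. Feasibility then needs thought: patients may enter from one week after an injury that caused coma, with consent from next of kin. If it is withdrawn, wording and a restated sample-size basis.

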The physical aspects of Radio Electric Asymmetric Conveyer (REAC) treatments involve a noninvasive interaction of low intensity RE emissions with the patient's body. The device features a unique ACP that convey the RE field to the target area. REAC treatments are non-invasive and painless. Patients typically lie or sit comfortably while the ACP is placed on specific areas of the body based on the treatment protocol. The treatment sessions duration can vary depending on the targeted condition and treatment plan. Overall, the physical aspects of REAC treatments involve the application of low power RE energy through a specialized probe to potentially influence cellular processes.

Adverse effects

No adverse effects have been reported to date. However, transient expected side effects that are part of the therapeutic response may occur, such as mild axial instability, asthenia, and mood swings.

Contraindications

At present, no specific contraindications to REAC neuromodulation treatments have been identified. However, it is recommended to avoid application in patients with pacemakers and pregnant women.

Ethical Aspects related to the use of REAC technology treatments.

Widespread axonal damage currently has no effective therapy. REAC neuromodulation treatments are safe and non-invasive and have been shown to

produce improvements in other neurodegenerative diseases. Based on these premises, there are no apparent ethical concerns.

Regulation

The devices used in this study are the BENE Model 110 devices, which have obtained both CE and ANVISA (Brazilian regulatory agency) certification.

Table 3 – Possible therapeutic applications for REAC in TBI

Therapeutics

Neuro postural optimization NPO and Neuro Psycho Physical Optimization – Brain Wave Optimization-G (NPPO-BWO-G) treatments
 
Enhance:
 
 • Motor recovery • Cognitive rehabilitation (memory, language, executive functions) • Treatment of post-concussion syndrome • Reduction of depression, anxiety, and post-traumatic stress symptoms • Treatment of chronic disorders of the level of consciousness • Painful syndromes

REAC in cognitive, mood, behavior, and motor disorders.

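### The only effects the protocol names for REAC are classed as therapeutic and have no scheduled collection, so the planned comparison of adverse effects between arms would miss them or count them inconsistently

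*Protocol*

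**What the plan says.** Three parts of the protocol bear on this.

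- **Adverse effects** (Literature Review, section on REAC). It first states "No adverse effects have been reported to date". The next sentence qualifies this: "transient expected side effects that are part of the therapeutic response may occur, such as mild axial instability, asthenia, and mood swings". No other unwanted effect of REAC is named in the document.
- **Statistical analysis.** "The comparison of the frequency of adverse effects according to the intervention groups will be performed using Pearson's chi-square". The protocol does not define an adverse effect for this count, and does not say whether the expected side effects enter it.
- **Table 7.** Step 1 is "qEEG, TCD and brain4care up to 3 days before the start of REAC sessions". Steps 2 and 3 list only the interventions: one NPO session and 18 NPPO sessions. Step 4 is "qEEG up to 3 days after the end of REAC sessions". Follow-up at discharge, 3 and 6 months consists of mRankin, GOSE and DASS 21.

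Table 6, Procedures and Outcomes add no safety assessment and no safety outcome. Recruitment and adherence strategies says that admission and in-hospital records will be collected, without describing this as a way of finding adverse effects.

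**The concern.** The planned test depends on what is counted and when it is looked for, and the protocol is weak on both.

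On what is counted, the only guidance is a sentence that attributes the three named effects to the treatment working. The sham arm is there to show whether REAC causes such effects and how often. Calling them therapeutic in advance presumes part of the answer and invites staff not to record them.

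On when, the effects are described as transient, yet no assessment is scheduled across the session days, when they would be expected. Spontaneous report is a weak substitute here: patients have had a coma of at least 6 hours, can enter from one week after injury, and are enrolled through next of kin.

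At stake is how the safety result can be read. A small count could reflect a well-tolerated device, or only the label and the schedule, and the data would not tell these apart. A later analysis plan could not repair this, because it cannot recover transient events that were never recorded.

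**Working it through.** **Step 1: the text side by side.** The protocol states no adverse-effect rate, so there is no figure to reproduce. The check is whether the three named effects have a route into the planned count.

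| Stage | Listed in the protocol | Route for instability, asthenia, mood swings |
|---|---|---|
| Step 1 | qEEG, TCD, brain4care | No baseline symptom record |
| Steps 2–3 | 19 sessions | None scheduled |
| Step 4 | qEEG | None scheduled |
| Discharge, 3m, 6m | mRankin, GOSE, DASS 21 | DASS 21 bears on mood only, and not at the time of the sessions |
| Throughout | In-hospital records | Incidental entries only |

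Capture is therefore partial and unstructured. It is not shown to be zero.

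**Step 2: what partial capture does to the test (illustration).** Inputs from the protocol: 36 participants at 1:1, so 36/2 = 18 per arm; 30 completers, so 30/2 = 15 per arm; alpha 5%. Assumptions: the true rates, a two-sided test, and a fraction c of affected patients recorded, equal in both arms. The recorded rates are then c × 40% and c × 10%. Power is the summed exact binomial probability of all outcomes for which the uncorrected Pearson chi-square gives p < 0.05.

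| c | Recorded rates | Power, 18 per arm | Power, 15 per arm |
|---|---|---|---|
| 1 | 40% vs 10% | 56% | 51% |
| 0.5 | 20% vs 5% | 25% | 19% |
| 0.25 | 10% vs 2.5% | 6% | 4% |

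The starting point depends heavily on the assumed rates. With full capture, 30% vs 10% gives 32% (18 per arm) or 28% (15 per arm), and 50% vs 10% gives 79% or 73%.

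**Step 3: what a zero count would mean (illustration).** If 0 of 18 active patients had a recorded effect, the one-sided 95% upper bound on the recorded rate is 1 − 0.05^(1/18) = 15.3%. The two-sided version is 1 − 0.025^(1/18) = 18.5%. The recorded rate is c times the true rate, so the one-sided bound on the true rate is 15.3%/c:

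- c = 1: 15.3%
- c = 0.5: 0.1533/0.5 = 30.7%
- c = 0.25: 0.1533/0.25 = 61.3%

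Because c is unknown under the present schedule, a zero or low count puts no usable limit on the true rate.

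**The case against.** The case on the other side has real force on several points.

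- *The sentence is background, not a recording rule.* It stands before Material and Methods, under the heading Adverse effects, and it uses the term side effects. An investigator could well count all three. This stands. A reader might infer that the comparison would certainly omit them; the text supports only that they would be missed or counted inconsistently.
- *The protocol does not claim that REAC has no adverse effects.* It says that none have been reported so far, which is a statement about past experience. This stands.
- *Something is collected.* In-hospital records exist, patients are recruited while hospitalised, Table 6 places REAC in the ICU, and DASS 21 touches mood. This stands; what is absent is dedicated collection timed to the sessions.
- *The trial is double-blind.* A reader might infer that the label hides harm in the active arm in particular. The documents do not support that, because it would apply to the same symptoms in both arms. With equal capture the ratio of rates is preserved while the difference shrinks (40 − 10 = 30 points becomes 20 − 5 = 15), so the result is lost sensitivity. Events other than the three are untouched by the label, although they too have no scheduled collection.
- *Adverse effects are neither a primary nor a secondary outcome, and power is modest even with full capture.* This is correct, and it limits the severity. The primary qEEG comparison is unaffected.

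None of this removes the central problem. The protocol commits to a between-arm comparison while its only guidance on these effects points towards excluding them, and its schedule does not look for them when they would be expected.

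**Conclusion.** The point holds in a limited form and should be fixed. The Adverse effects paragraph and the Statistical analysis section need to be reconciled, and Table 7 has no collection step to support the planned test. As written, the three named effects would be missed or counted inconsistently in both arms. The chi-square comparison would lose sensitivity, and a low count would not be evidence of safety.

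The size of the loss is unknown. The documents give neither a rate for these effects nor a capture fraction, so the power figures and bounds above show direction only and rest on assumed values. The conclusion itself rests on the text: the classification, the planned test and the schedule.

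**What to change.** 1. **Adverse effects paragraph.** Delete the clause that assigns these effects to the therapeutic response. State that any new or worsened unfavourable sign or symptom from the first session onward counts as an adverse effect in both arms, whatever its presumed mechanism.
2. **Table 7.** Add a short checklist (axial instability, asthenia, mood swings, other), completed by existing staff who are blinded to allocation. Schedule it at Step 1 as baseline, on each session day in Steps 2 and 3, at Step 4, and at discharge, 3 and 6 months. The baseline entry is needed so that symptoms already present after the injury are not counted as new.
3. **Population.** Use the same checklist for the DAI patients and for the volunteers without neurological disease, who undergo the same protocol.
4. **Statistical analysis.** Name the DAI patients' checklist record as the source for the between-arm comparison.

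Cost: at the Abstract's maximum of four sessions a day, 19 sessions take at least five days (19/4 = 4.75). That makes at least 1 + 5 + 1 + 3 = 10 short forms per participant, and more if sessions are spread out. No added procedures or patients are needed. The reported adverse-effect rate will probably look less favourable than it would without active collection.
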